	population using a Kaplan Meier estimator/curve.

2. Schedule of Events (Table 1)

			Table 1						
			Treatment (28-day/4-week cycles, ±1-day)						
Study Procedures	Screening Period up to 3 weeks	Up to 5-8 days prior to C1D1	C1D1	C1D8	C1D15	C1D22	D1 and D15 on subsequent cycles	End of Treatment Visit (+/- 7 days)	Follow up (every 8 wks, ± 1 week)
Informed consent	Х								
Eligibility criteria	Х		Х						
Demography	Х								
Medical history	Х								
Concomitant Medications Collection	Х		Х		Х		Х		
Physical exam (including height [screening only] and weight)	х		х	х	х	х	Х	Х	
Vital signs (temperature, BP, and heart rate)	Х		Х	Х	Х	Х	Х	Х	
Performance status [1]	х		Х	х	х	х	Х	х	
12-Lead ECG	Х		X[2]		X[2]			Х	
Radiological assessments (CT or MRI) [3]	х	X (every 8	weeks [±3	days] fro	om time c	of enrollm	nent until disease	progression, or death)	
AEs/SAEs [14]	X (collected from the time of informed consent until 30 days after the last study treatment)								
Blood phenotype [4]	X[4]								
Prescription with current weight		X[5]	X[5]		X[5]		X[5]		
Irregular antibody screening test (IAST) [6]	X[6]		X[6]		X[6]		X[6]		
Pre-eryaspase dose complete compatibility test [7]			X[7]		X[7]		X[7]		
Eryaspase administration [8]			X[8]		X[8]		X[8]		
FOLFIRINOX			Х		Х		Х		
Hematology, biochemistry, and coagulation panels; CA19-9 [9]	X[9,10]		х		х		Х	Х	
Pregnancy test, for patients of childbearing potential [11]	х		Х		х		Х	х	
Survival follow-up									X[13]
Subsequent anti-cancer treatments									х

Tables abbreviations and legends:

D=Day; BP=blood pressure; ECG=electrocardiogram; CT=computed tomography; MRI=magnetic resonance imaging; IAST=irregular antibody screening test; CA19-9=cancer antigen 19-9; ASPNase = Asparaginase. [1] According to the Eastern Cooperative Oncology Group (ECOG)

[2] Performed pre-dose Cycle 1 Day 1 and Day 15

[3] Radiological assessment (CT C/A/P) to be completed within 3 weeks of screening and then every 8 weeks (±3 days) from the time of enrolment until disease progression or until withdrawal from the study treatment, or death, using the same method throughout.

[4] A complete erythrocyte phenotype (including D, C, E, c, e, and K antigens), ABO blood group status, and

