[11] For patients of childbearing potential, serum pregnancy test to be performed during the screening period and at End of Treatment and urine/serum pregnancy test to be performed prior to dosing of any chemotherapy agent
[13] Survival follow to be conducted by phone, visit, or medical records review every 8 weeks (± 1 week) from end of treatment visit until patient's death, loss to follow up, or study closure. Subsequent therapy should be collected during this follow up.

Additional lab tests may be required (e.g., weekly monitoring per standard practice or label requirements should be followed) and should be reported if clinically significant

[14] SAEs are not required to be reported until after they received the first dose.

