- Adverse event(s) that, in the judgment of the investigator, may cause severe or permanent harm or which rule out the continuation of study drug
- General or specific changes in the patient's condition render the patient unacceptable for further treatment in the judgment of the investigator
- Suspected pregnancy
- Serious non-compliance with the study protocol
- Lost to follow-up
- Patient withdraws consent
- Investigator removes the patient from the study
- The Sponsor-Investigator or Georgetown decides to close the study

After 12 treatments of FOLFIRINOX, patients have the option to continue FOLFIRINOX plus Eryaspase or can transition to FOLFIRI (dropping Oxaliplatin) plus Eryaspase or 5-FU (dropping Irinotecan and Oxaliplatin) plus Eryaspase, at the investigator's discretion.

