5.9 Duration of follow-up

Patients will be followed via chart review or phone interview every 8 weeks for a total of 2 years or until death, whichever occurs first. Patients removed from study for unacceptable adverse events will be followed until resolution or stabilization of the adverse event.

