7.1 Screening and Enrollment

For patients being considered for enrollment outside of Georgetown-Lombardi, all primary source documentation should be sent to Georgetown University's Multicenter Project Management Office, and the principal investigator, [name], for review and approval. Patients must be approved for accrual prior to starting study medications. Patient IDs will be assigned at the time of registration.

Informed consent must be obtained prior to the performance of study related evaluations.

Within 21 days prior to study entry subjects will undergo the following evaluations:

- o Demographics, medical history, and concomitant medications
- o A physical exam, height, and weight measurements
- Vital signs including temperature blood pressure and heart rate
- o A 12-lead ECG will be obtained
- Subject performed status will be assessed via the ECOG scale
- Samples will be collected for serum chemistry hematology, coagulation, and CA-19-9
- Irregular antibody screening test (IAST)
- Blood phenotype
- Radiographic assessments will be obtained during screening and then repeated every 8 weeks from the time of enrollment until disease progression or death

7.2 Study Day -8 to Day -5

The following procedures will be performed at least 5 days prior to Cycle 1 Day 1:

• Prescription with current weight

7.3 Study Day 1

The following procedures will be performed:

- Physical examination
- Vital signs including temperature blood pressure and heart rate
- Subject performed status will be assessed via the ECOG scale
- o 12-lead ECG
- Pre-Eryaspase dose complete compatibility test
- Irregular antibody screening test (IAST)
- Samples will be collected for serum chemistry hematology, coagulation, and CA 19-9
- For all women of childbearing potential, a urine pregnancy test will be administered
- Eryaspase Administration
- FOLFIRINOX Administration

7.4 Study Day 8

The following procedures will be performed:

- Physical examination
- o Vital signs including temperature blood pressure and heart rate
- \circ Subject performed status will be assessed via the ECOG scale
- o All adverse events will be recorded

7.5 Study Day 15

The following procedures will be performed:

- Physical examination
- o Vital signs including temperature blood pressure and heart rate
- \circ Subject performed status will be assessed via the ECOG scale
- All adverse events will be recorded
- o 12-lead ECG
- Pre-Eryaspase dose complete compatibility test

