7.8 End of Treatment/Safety Follow-up

Subjects will complete an end of treatment (EOT) evaluation 4 weeks (+/- 7 days) after the last day of treatment on study or after tumor progression is documented. In addition, a positive urine test must be confirmed by a serum pregnancy test.

Survival follow up will be conducted by phone, visit, or medical records review every 8 weeks $(\pm 1 \text{ week})$ from end of treatment visit until patient's death, loss to follow up, or study closure. Subsequent anti-cancer treatment should be collected during this follow up.

8 Study Assessment

8.1 Efficacy Assessments

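### Table 1 footnote 3 ends 8-weekly scans when study treatment is withdrawn, while the table row and section 7.1 continue them to progression or death (minor)

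*Combined protocol and SAP*

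**What the plan says.** Three places in the protocol say when 8-weekly imaging ends.

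- Table 1, footnote 3: scans continue "until disease progression or until withdrawal from the study treatment, or death, using the same method throughout".
- Table 1, radiology row (the row that footnote 3 annotates): the end points are progression or death. Treatment withdrawal is not listed.
- Section 7.1: scans are "repeated every 8 weeks from the time of enrollment until disease progression or death".

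Section 5.8 gives routes off treatment that are not progression. They include an adverse event that "may cause severe or permanent harm or which rule out the continuation of study drug" and changes in condition that "render the patient unacceptable for further treatment in the judgment of the investigator". Table 4C adds that a grade 4 non-hematologic toxicity ends all protocol treatment.

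For the period after treatment, section 7.8 states: "Survival follow up will be conducted by phone, visit, or medical records review every 8 weeks". Table 1 note 13 adds: "Subsequent therapy should be collected during this follow up". Section 5.9 states: "Patients will be followed via chart review or phone interview every 8 weeks". None of these mentions imaging. Section 8.1.1 covers measurement methods only. Section 11.3 plans a Kaplan-Meier summary of PFS and gives neither a PFS definition nor a censoring rule.

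**The concern.** A patient who stops for toxicity or decline, with no progression yet recorded, falls under two different instructions. Under footnote 3 the scans stop. Under the table row and 7.1 they continue every 8 weeks. Two sites could each follow the protocol and handle the same patient differently, and a scan that was not taken cannot be recovered at analysis.

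What is at stake is PFS, a secondary objective. If scans stop with treatment and the patient is censored at the last on-treatment scan, Kaplan-Meier assumes that this patient's later risk matches that of patients still under scan. For someone who stopped because of worsening condition this is doubtful, and the curve would then lie too high. If stopping has nothing to do with impending progression, the assumption holds and the only loss is fewer patients at risk.

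**Working it through.** **Textual check**

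| Place | Ends at progression | Ends at death | Ends at treatment withdrawal |
|---|---|---|---|
| Table 1, radiology row | yes | yes | no |
| Table 1, footnote 3 | yes | yes | yes |
| Section 7.1 | yes | yes | no |
| Note 13, 5.9, 7.8 | no imaging rule | no imaging rule | no imaging rule |

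No sentence gives one of these precedence. The plan states no figure on this point, so there is none to reproduce.

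**Illustration of size (assumed inputs)**

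From the documents: scan interval 8 weeks (56 days, 1.84 months); 12-19 patients most likely (5.2). Assumed: 10-30% of patients stop without progression; median time to progression 5 or 8 months, exponential; censoring at the last on-treatment scan. Deaths before progression are not modelled.

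1. Progression risk per scan interval: h = 1 - exp(-ln 2 × 1.84 / median). This is 0.2251 (5 months) and 0.1474 (8 months).
2. True 24-week PFS, three intervals: (1 - h)³ = 0.7749³ = 46.5% and 0.8526³ = 62.0%.
3. Suppose a share f of progressing patients stops just before the scan that would have shown it. In each interval a fraction fh leaves the risk set uncounted, so the Kaplan-Meier factor becomes (1 - h)/(1 - fh). For f = 0.30 and a 5-month median: 0.7749/(1 - 0.0675) = 0.831, and 0.831³ = 57.4%.

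| f | 24-week PFS, 5-month median | Shift (points) | 24-week PFS, 8-month median | Shift (points) |
|---|---|---|---|---|
| 0 | 46.5% | 0 | 62.0% | 0 |
| 0.10 | 49.8% | 3.3 | 64.8% | 2.8 |
| 0.15 | 51.6% | 5.1 | 66.3% | 4.3 |
| 0.30 | 57.4% | 10.9 | 71.0% | 9.0 |

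The rows f = 0.10 and f = 0.30 are the worst case at each end of the assumed range, where every early stop falls just before progression.

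4. Mixed case: a 30% stop rate, half just before progression and half independent of it. Simulation gives 52.0% and 66.7%, shifts of 5.5 and 4.7 points. With all 30% independent, it gives 46.5% and 62.0%, no shift.
5. Standard error of 24-week PFS without censoring, √(S(1 - S)/n), for n = 12 and 19: 14.4 and 11.4 points at 46.5%; 14.0 and 11.1 points at 62.0%. The largest shift is 10.9/11.4 = 0.95 of a standard error at n = 19 and 10.9/14.4 = 0.76 at n = 12.
6. Patients concerned: 12 × 0.10 = 1.2 to 19 × 0.30 = 5.7, so about 1 to 6.

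**The case against.** The best defence is that the post-treatment text points one way. The follow-up provisions in note 13, 5.9 and 7.8 can be met by telephone or records, and none names a scan. Section 7.1 is a screening list that mentions later scans in passing, whereas footnote 3 is the detailed note attached to the imaging row. On that view 7.1 is shorthand and footnote 3 is the rule. This stands in part: practice would probably lean towards footnote 3. It does not remove the contradiction, because the table row itself omits treatment withdrawal and nothing sets precedence. If footnote 3 is the intended rule, the plan has chosen the version that leaves progression unobserved.

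Aligning the other two places with footnote 3 would also remove the inconsistency. That is true, but it would settle the matter in the direction that can bias PFS.

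The size is entirely assumed, and it also needs censoring at the last on-treatment scan, which no section states. Deaths are tracked in follow-up under either rule, and record review might reveal progression found in routine care, although the plan does not require it. All of this stands and limits the point.

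A reader might infer that many patients leave imaging at about six months, since 5.8 says "After 12 treatments of FOLFIRINOX, patients have the option to continue FOLFIRINOX plus Eryaspase". The documents do not support that. The alternatives named there, FOLFIRI or 5-FU, also keep eryaspase, so the patient stays on study treatment and is scanned under either rule. Stopping is possible at that point, but no rate can be taken from the text.

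**Conclusion.** The contradiction is real and unresolved in the current text. Its consequence is small. The direction of bias is upward only if stopping is related to decline. If it is not, there is no shift. Under the assumed 10-30% early stopping and 5- or 8-month medians, the worst case is about 3 points at the low end and 9-11 at the high end, and at most about one standard error for 12-19 patients.

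A reader might infer that the PFS results would be materially misleading, or that the dose finding is compromised. Neither is supported. Section 11.3 presents PFS descriptively with no hypothesis tests, the true stopping pattern is unknown, and MTD and DLT decisions use first- and second-cycle toxicity and treatment delay, not imaging after treatment. Severity is minor. It is worth correcting because one procedure has two instructions.

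**What to change.** Delete the treatment-withdrawal clause from Table 1 footnote 3, so that it matches the row it annotates and section 7.1. Add a sentence to 7.8 that patients who stop treatment without progression continue 8-weekly scans until progression, death or withdrawal of consent.

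The cost is two wording changes and some off-treatment scans in a small number of patients (about 1 to 6 under the assumed stop rates). The table row and 7.1 already require those scans.

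Whether PFS should be censored at the start of new anticancer therapy, and whether scanning should end there, is a separate choice and not part of this change.

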3. INTRODUCTION

3.1 Background

Pancreatic cancer is a highly aggressive malignancy. In the United States, there will be an estimated 55,440 new cases of pancreatic cancer diagnosed in 2018, with the disease causing an estimated 44,330 deaths. The estimated 5 year survival is poor at 8.5 %^{1,4} with a median survival of 10 to 12 months². The poor prognosis for pancreatic cancer is related to a combination of late detection, as most patients present with locally advanced or metastatic disease; and standards of care that consist of relatively ineffective chemotherapeutic regimens. Surgical resection is the only curative treatment for pancreatic cancer, however, only 15-20% of patients present with operable disease^{5,6}.

Improving survival in metastatic or unresectable disease remains a challenge; for decades many chemotherapy trials were conducted, however, most failed to demonstrate efficacy. For the past decade, we had only two studies that showed meaningful small improvements in survival and changed the practice. The PRODIGE4/ACCORD 11 trial compared FOLFIRINOX (fluorouracil with irinotecan hydrochloride, leucovorin calcium, and oxaliplatin) to single-agent gemcitabine in patients with metastatic pancreatic cancer. FOLFIRINOX demonstrated a significant survival advantage; median overall survival (mOS) of 11.1 months (m) vs. 6.8 m (HR Version 2.1, 16 March 2022

0.57, P <0.001,)². While the MPACT trial evaluated gemcitabine/nab-paclitaxel combination to gemcitabine alone in patients with metastatic pancreatic cancer, nab-paclitaxel was associated with improved survival; mOS of 8.5 m vs. 6.7 m (HR 0.57, P <0.001)⁷. Unfortunately, since these studies, we have not made any new progress that has changed the outcome of this devastating disease. Hence, new therapeutics that provide greater clinical efficacy in patients with pancreatic cancer are urgently needed.

KRAS (Kirsten rat sarcoma virus) mutations are observed in more than 90% pancreatic ductal adenocarcinomas (PDAC)^{8,9}. KRAS mutations provoke a constitutive activation of RAF/MEK/ERK and PI3K/AKT-mTOR pathways, reprogramming of metabolic pathways that allow continued cellular proliferation in the absence of nutrients required by normal cells^{10,11}. Consequently, targeting cell metabolism is a novel approach in pancreatic adenocarcinoma¹².

What distinguishes the pancreatic tumor cell's metabolism from normal cells is the dependence on metabolites that are utilized through the non-canonical metabolic pathway¹³. The amino acid glutamine, for instance, has an essential role in sustaining anabolic metabolism and biosynthetic pathways, including the de novo synthesis of asparagine^{14,15}. Asparagine is a non-essential amino acid, synthesized intracellularly from glutamine and aspartic acid by the enzyme asparagine synthetase (ASNS). However, this biosynthesis capacity varies between cells¹⁶.

3.2 Preclinical Data

In leukemic cells, the asparagine synthetase (ASNS) is lacking, therefore, it depends on circulating asparagine in the serum¹⁷. The modulation of glutamine and asparagine metabolism was targeted with L-Asparaginase (L-ASNase). L-ASNase induces an antineoplastic effect through catalyzing the asparagine to ammonia and aspartic acid, consequently, depletion of serum asparagine leading to cycle arrest and cell death. Moreover, ASPNase deplete the serum glutamine as it acts as a substrate for the enzyme, and thus contributing further to cell growth inhibition and apoptosis¹⁸. Hence, L-ASNase has been tested and used in pediatric acute lymphoblastic leukemia (ALL) and has become one of the cornerstone components of chemotherapy regimens used in ALL.

Interestingly, ASNS expressions are high in normal pancreatic cells. However, more than 50% of pancreatic adenocarcinoma has low or no expression of ASNS^{19,20}. Therefore, the modulation of glutamine and asparagine metabolism has become an investigational therapeutic strategy of interest in pancreatic cancer. Unfortunately, L-ASNase has a narrow therapeutic index and was correlated with significant toxicity when it was tested in solid tumors, including pancreatic cancer²¹.

Eryaspase is an encapsulated *Escherichia Coli* L-ASNase within erythrocytes. It's a novel way of delivering L-ASNase that led to the delivery of effective doses with less toxic effects. Encapsulation of L-ASNase decreases the rapid degradation of L-ASNase in the blood, thus prolonging activity, with a half-life of approximately two weeks. Furthermore, encapsulation limits exposure to the immune system and, subsequently, decreases its intrinsic immunogenicity and hypersensitivity reactions²².

3.3 Previous Human experience

Encapsulated L -asparaginase within erythrocytes investigated in GRASPALL 2005 phase I/II, a multicenter randomized controlled trial, investigated the safety profile of three dose levels (50, 100, and 150 IU/kg). The study results suggested a reduction in the number and severity of allergic reactions and a trend towards fewer coagulation disorders. Other adverse events were comparable to those observed with E. coli L-asparaginase, and there was also no difference between the three doses²².

In pancreatic cancer, two clinical trials have been conducted. The first clinical trial in pancreatic cancer was GRASPA 2008 trial (NCT01523808), a national, multicenter, open-label, phase 1 dose-escalation study, which investigated Eryaspase as a single agent in patients with metastatic pancreatic cancer progressed after two lines of therapy. Twelve patients were enrolled, and they received a single administration of Eryaspase as monotherapy (25, 50, 100, or 150 IU/Kg). No dose-limiting toxicity was reported. The recommended Phase 2 dose was determined to be 100 IU/Kg every two weeks²³.

Subsequently, a Phase 2, multicenter, open-label trial investigating Eryaspase in combination with gemcitabine or mFOLFOX6 (modified FOLinic acid-Fluorouracil-Oxaliplatin-6 regimen) as second-line treatment in patients with metastatic pancreatic cancer was conducted. The trial was completed in 2017. The endpoint of the study was an improvement in progression-free survival (PFS) or overall survival (OS) in patients with no or low ASNS (0/1) expression as determined by immunohistochemistry (IHC), with a target hazard ratio (HR) < 0.85. Secondary endpoints included OS, PFS, objective response rate, safety, and QoL. A total of 141 patients were enrolled and randomized, 95 to Eryaspase plus chemotherapy and 46 to chemotherapy alone. The majority of patients (90%) received gemcitabine during the study. Both co-primary endpoints were met in the ASNS 0/1+ subgroup (Eryaspase, n= 66; control, n= 32), with HRs of 0.67 for PFS and 0.63 for OS³. These encouraging results prompted investigators to plan for the Phase III study. However, we sought to test the safety and tolerability of Eryaspase with FOLFIRINOX, the current first line, and standard of care chemotherapy.

Eryaspase's safety and efficacy also have been under investigation in other clinical trials, acute lymphoblastic leukemia (ALL)²⁴ and acute myeloid leukemia (AML)²⁵.

3.4 Study Rationale

As previously mentioned, the treatment options for unresectable and metastatic pancreatic cancer remain limited with poor survival. As such, there is a great need for further drug development. In the previous phase II second-line trial the combination of Eryaspase plus gencitabine or Eryaspase plus FOLFOX was superior to that of chemotherapy alone. Given this preliminary efficacy signal, and this trial is designed to perhaps demonstrate an even larger signal of efficacy in the first-line setting. FOLFIRINOX is the standard of care for the first-line treatment of patients with the unresectable disease worldwide and thus justifies our combination of FOLFIRINOX plus Eryaspase.

3.5 Justification for Dose

We plan to use modified dosing of FOLFIRINOX which has been an accepted practice across recent clinical trials, the infusion 5-FU, Oxaliplatin and are given at a full dose. The Irinotecan

is given at a modified dose in order to minimize Gastrointestinal and hematologic toxicity, and the bolus 5-FU is eliminated in order to minimize myelosuppression. Eryaspase has been previously evaluated in twelve patients at dose levels 25. 50. 100 and 150 units/kg without evidence of a dose limited toxicities. The recommended phase 2 dose was 100 units/kg. We will start with a dose of 75 units/kg, with the goal of reaching 100 units/kg, however, will also build in a -1/-2 dose level of 50/25 units /kg.

4. **Objectives**

4.1 Primary Objective

• The primary objective of this study is to determine the maximum tolerated dose, tolerability and safety of Eryaspase in combination with the dose-modified FOLFIRINOX in patients with newly diagnosed locally advanced or metastatic pancreatic adenocarcinoma.

4.2 Secondary Objectives

- To estimate the objective response rate (ORR)
- To summarize progression-free survival (PFS)
- To summarize overall survival (OS)

5. Study Design

5.1 Overall Design

This is an open-label, multicenter, Phase 1 study of Eryaspase combination with FOLFIRINOX in patients with locally advanced or metastatic pancreatic adenocarcinoma. Subjects will undergo screening in order to determine eligibility. The screening period will not exceed 28 days. Eligible patients will receive Eryaspase and it will be administered on Day 1 and 15 of the 4-week cycle combined with mFOLFIRINOX.

5.2 Sample Size

The sample size for the standard 3+3 design is random with a total of anywhere from 9 to 21 subjects possible, but 12-19 subjects most likely, with at most 1 escalation level and 2 de-escalation levels beyond the initial dose level.

5.3 Cohorts/Escalation scheme

